### **Data Management and Monitoring**

Enrollment and case record forms will be completed for each study subject. Their initials and study code on the case record form will be used to identify the participants. The principal investigator will be responsible to complete case record forms at each visit. All corrections will

be made on the case record form by striking through the incorrect entry with a single line and entering the correct information adjacent to it.

All clinical data will be recorded onto standardized case record forms by the principal investigator. Laboratory data will be recorded in a laboratory record book by the laboratory technician and then transferred to the case record forms by the principal investigator. Data will be transferred from the case record forms into a computerized database (IBM SPSS Version 26, WHO excel sheet and plain excel spread sheet). The WHO excel sheet is specially designed for the analysis of efficacy study data and it only performs the analysis when double entry is assured to verify accuracy of entry. Two backup files and the database will be stored on compact discs after each data entry session.

Members of the central team (co-advisor) from EPHI will supervise the overall study progress of the study and reviewed all data records at the mid of the study period. All study record forms will be checked for completeness and accuracy. In addition, daily communication will be made with the members of the central team (co-advisor, other study team members).

### **Data Quality Control**

The health personnel's (Medical Doctor, Health Officer, laboratory technician, and nurse (tracer)) involved in the study will be oriented on the use of the study procedure; following the in vivo study protocol designed by the World Health Organization WHO). Prior to the study, the laboratory technician will have a refresher training to ensure proper preparation of blood smear, correct identification of parasites and accurate parasite counting. Giemsa stock solution and working solution will be prepared at EPHI laboratory.

Microscopic results will be assessed following the procedure that emphasizes reproducibility of final outcome classification over reproducibility of exact parasite counts by crosschecking 10% of the total slides. To avoid errors in recording data, the study supervisors on a regular basis will review all case report forms during the assessment for completeness and accuracy.

Data will be entered into compute double entry using WHO data analysis excel sheets and SPSS version 26 and a random sample of 10% of computerized records will be selected and compared to hard copy case report forms for confirmation of consistency.

## Statistical Analysis

Every data from recruited patients will be imported into the WHO Excel sheet (double entry) which is designed for analysis of therapeutic efficacy study data. Data will be also entered in to IBM SPSS (version-26) software to calculate descriptive statistics (mean, median, standard deviations, range). Independent sample t-test will be used to compare baseline temperature and parasitemia between children and adults; mean blood Hb level at D0, D14, D28 and D42 between patients with parasitemia  $\geq 10,000$  and  $< 10,000/\mu\text{l}$  blood. Non-parametric (median) test for independent sample will be used to compare D1 parasitemia between children and adults and paired sample t-test will be used to compare mean Hb level between D0 and D14, D0 and D28, D14 and D28, D0 and D42, D28 and D42. All comparisons will be performed at 95% CI and significance level of 0.05.

Kaplan Meier (K-M) survival analysis and per protocol (PP) analysis will be used for estimation of primary outcomes and PP analysis method will be used to analyze secondary outcomes. The K-M survival analysis method provides better approximation of cure rates as it incorporates probabilities for censored data (incomplete observations due to LFU and withdrawals) in to the analysis. The WHO excel sheet is especially designed for estimation of cure rate based on K-M survival estimator analysis method.

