## Sample Size Determination and Sampling Technique

### Sample Size Determination

The sample size will be determined according to the WHO (2009) protocol(11); by using the single population proportion formula and calculated assuming 5% margin of error, 95% confidence interval (CI), and treatment failure of 5% and 20% loss to follow-up rate. Accordingly, a minimum of 73 patients will be enrolled.

$$\text{Sample size (n)} = \frac{[(Z \alpha/2)^2 p(1-p)]}{d^2}$$

$$\frac{(1.96)^2 0.05 (1-0.05)}{(0.05)^2} = 73$$

Assuming an additional 20% loss to follow-up rate and withdrawal of consent (15 patients) during the study, at least 88 (73 + 15) patients will be required to bring about a representative sample size.  $n = (1+0.2) 73 = 88$  Where, n= sample size

P=Expected treatment failure (5%)

Z=confidence interval (95%)

d=margin of error (5%)

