### **Study Variables**

#### **Independent Variables**

- Age, Sex, Weight, Axillary temperature, leukocyte count, asexual and/ or sexual parasites count, Hemoglobin count

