### Laboratory Examination

**Microscopic blood examination:** thick and thin blood smears will be taken from all participants and prepared on the same slide for detection of parasites at all time-points during the 42-day follow-up period. Two smears will be prepared in each case; the first will be stained rapidly with 10% Giemsa for 10–15 min for initial screening and examined by light microscopy immediately. On day 0, in order to rapidly confirm adherence to the lowest parasite density considered for enrollment, initial screening of patients will be made in 10% Giemsa-stained thick film after counting at least 1 parasite for every 6-8 WBCs, which corresponds to approximately 1000 parasites/ $\mu$ l.

The second one will be stained slowly with 3% Giemsa 45–60 min to be examined later by an experienced technician to provide definitive parasite count and speciation. The below formula will be used to determine parasite density.

$$\text{Parasite density (per } \mu\text{l)} = \frac{\text{number of parasites counted} \times (6000-8000)}{\text{Number of leukocytes counted} \approx 200}$$

Two experienced laboratory technicians will examine slides independently. Parasite densities will be calculated from thick blood smears by counting the number of asexual parasites against 200 WBC. If the count is <10 parasites/200 WBC, at least 500 WBC will be counted. A thick blood smear will be declared negative if no parasites are seen in 1000 WBCs and mixed infection has been excluded in 100 fields on thick film. Gametocytes will be detected and counted in thick film. Thin blood smears will be examined to determine parasite species. Gametocytes will be counted in thick blood films against 2000 WBCs.

Two qualified microscopists will read all the slides independently, and parasite densities will be calculated by averaging the two counts. Blood smears with discordant results (differences between the two microscopists in species diagnosis, in parasite density of > 50% or in the presence of parasites) will be re-examined by a third, independent microscopist, and parasite density will be calculated by averaging the two closest counts.

**Hemoglobin:** The hemoglobin concentrations will be measured using a portable spectrophotometer (HemoCue®, Anglom, Sweden), on days 0, 14, 28, and 42.

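### The Hb comparison by parasite density uses a two-group split and separate visit-by-visit t-tests, so it discards the continuous count and cannot show whether Hb change differs by density

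*Combined protocol and SAP*

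**What the plan says.** The Statistical Analysis section opens its list of tests with "Independent sample t-test will be used to compare baseline temperature and parasitemia between children and adults", and the same sentence goes on to Hb: "mean blood Hb level at D0, D14, D28 and D42 between patients with parasitemia" of at least 10,000/µl and those below it. The plan does not say which day's parasitaemia defines the groups; day 0 is presumed here.

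The only other Hb analysis is within patients: "paired sample t-test will be used to compare mean Hb level between D0 and D14, D0 and D28", followed by three further pairs of days. Those five paired tests pool all patients and do not involve the density groups. For testing, "All comparisons will be performed at 95% CI and significance level of 0.05", and "PP analysis method will be used to analyze secondary outcomes". No regression, analysis of covariance, between-group comparison of change or repeated-measures model is named.

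The data for a fuller analysis are already collected. Under Laboratory Examination, Hb is measured "on days 0, 14, 28, and 42", and density is a count averaged over two independent readers. The Independent Variables section lists "Age, Sex, Weight, Axillary temperature, leukocyte count, asexual and/ or sexual parasites count, Hemoglobin count", but no planned model uses that list.

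**The concern.** Annex 1 admits densities from 250 to 100,000/µl, a 400-fold range (100,000 / 250). Under the plan, patients at 300 and 9,900/µl are treated as alike, while patients at 9,900 and 10,100/µl are treated as different. Each follow-up visit is then tested separately, as if nothing were known of the patient's starting Hb.

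A reader of the results is likely to ask whether patients with heavier parasitaemia gain Hb differently over 42 days. The four between-group tests address level on a given day. The five paired tests address change, but not by density. Neither set answers the question, and comparing the p-values of the separate visit tests does not answer it either. At stake are the precision and interpretability of a secondary result.

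**Working it through.** **The plan's own figure.** Sample Size Determination gives 1.96² × 0.05 × 0.95 / 0.05² = 72.99, rounded up to 73 ("a minimum of 73 patients will be enrolled"), and 73 × 1.2 = 87.6, rounded up to 88. Both reproduce. They rest on the precision of a failure proportion. No Hb standard deviation (SD), effect size, correlation or expected share above 10,000/µl is stated, so those are assumed below, and n = 73 is used for illustration.

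**Step 1: loss from the split.** Assume log density is normal and linearly related to Hb. With a share p of patients on one side of the cut, and φ the standard normal density at that cut, the information kept is φ² / [p(1 − p)]:

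| Split | Information kept | Equivalent patients out of 73 |
|---|---|---|
| 50:50 | 0.637 | about 46 |
| 30:70 | 0.576 | about 42 |
| 20:80 | 0.490 | about 36 |

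Eligibility truncates density at the low end, so normality can only be approximate.

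**Step 2: day-0 Hb as a covariate.** If ρ is the correlation between day-0 and follow-up Hb, residual variance is multiplied by 1 − ρ². For a two-sided 5% test, 80% power and a 50:50 split, the detectable difference is (1.960 + 0.842) × √(1 − ρ²) × √(1/36.5 + 1/36.5), in SD units:

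| ρ | Variance reduction | Detectable difference | Power for 0.6 SD |
|---|---|---|---|
| unadjusted | 0% | 0.66 SD | 73% |
| 0.3 | 9% | 0.63 SD | 77% |
| 0.5 | 25% | 0.57 SD | 84% |
| 0.7 | 49% | 0.47 SD | 95% |

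These figures take the adjusted difference to equal the unadjusted one, and they ignore the small loss of precision when day-0 Hb differs between the groups.

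**Step 3: change by density.** With equal SDs at the two visits, change from day 0 has variance 2(1 − ρ) times that of a single visit: 1.4, 1.0 and 0.6 at ρ = 0.3, 0.5 and 0.7. A density-by-visit estimate is therefore not always more precise than a single-visit comparison. Its merit is that it addresses change. The variance reductions in Step 2 belong to a regression that conditions on day-0 Hb.

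**The case against.** The strongest case on the other side is that nothing in the plan is wrong as written. It compares mean Hb levels by day, and a t-test is valid for that. Hb recovery is not named as an outcome under Dependent Variables, Classification of Treatment Outcomes or Safety endpoints. This stands.

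A reader might infer that the tests mix baseline differences with recovery, so that a day-0 gap would pass for an effect of parasitaemia. The documents do not support that. Day 0 is in the planned set, so a starting gap would be reported beside the later ones, and no text says the later gaps will be read as recovery. Nor is adjustment simply a correction. Suppose a 0.8 g/dl gap on day 0 with ρ = 0.6 and equal SDs (all assumed). It leaves 0.8 × 0.6 = 0.48 g/dl at follow-up when there is no difference given starting Hb. Yet the lower group has then gained 0.8 − 0.48 = 0.32 g/dl more, which is a difference in change. The groups are not randomised, and day-0 Hb is measured while parasites are present and may already reflect them. Conditioning on it therefore changes the question.

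A reader might also call the cut arbitrary. The plan gives no reason for it, but Annex 6 uses a parasite count above 10,000 in defining severe malarial anaemia, so the documents already link this threshold with Hb. Grouped means at that cut are a reasonable description.

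Finally, the size of any gain is assumed. At ρ = 0.3, power for 0.6 SD moves only from 73% to 77%, so a general claim of much lower power would go too far. What survives the objection is that the continuous count and the pairing with day 0 go unused in the between-group analysis, and that no planned analysis relates density to Hb change.

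**Conclusion.** The point holds as a minor improvement to a secondary analysis. The planned t-tests are valid descriptions of mean Hb by day. They keep roughly 64% (median split) to 49% (20/80 split) of the information in the count, given normal log density and a linear relation to Hb. They forgo a reduction in residual variance of 9% to 49% for correlations of 0.3 to 0.7, and they cannot show whether Hb change differs by density. The stronger conclusions, that the tests are confounded or badly underpowered, are not established: the plan makes no recovery claim, it reports the day-0 gap, and it gives no correlation, SD or group share from which power could be computed. The Kaplan-Meier and per-protocol cure-rate estimates and the sample size are unaffected.

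**What to change.** Amend the Statistical Analysis section as follows.

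- Fit one mixed model of Hb at D0, D14, D28 and D42 on log day-0 density (continuous), visit and their interaction, with age and sex as covariates. Report the density-by-visit estimates with 95% confidence intervals. Age and sex belong in the model because enrolment runs from over 6 months into adulthood and both are listed independent variables.
- Optionally add a regression of follow-up Hb on log density and D0 Hb, labelled as the association given starting Hb and not as a causal effect.
- Keep mean Hb above and below 10,000/µl at each visit as a descriptive table.
- State that the parasitaemia is the day-0 count.

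The cost is wording and analysis time. No new measurement, visit or patient is needed. The downside is that the model assumes linearity in log density, which should be checked, and that it answers a different question from the raw means, which is why both should be shown.

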#### Exclusion Criteria

- ♣ Severe malaria with complication sign and symptoms (see Annex I)
- ♣ Signs or symptoms of severe malnutrition, defined as weight-for-age  $\leq$  3 standard deviations below the mean, symmetrical edema involving at least the feet, or mid-upper arm circumference <100 cm for children less than five years of age (NCHS/WHO normalized reference values; see Annex I)
- ♣ Mixed plasmodium infection
- ♣ Severe anemia, defined as hemoglobin (Hb) < 8 g/dl

- ♣ Presence of febrile conditions caused by diseases other than malaria (e.g. measles, acute lower respiratory tract infection, severe diarrhea with dehydration)
- ♣ Serious or chronic medical condition (e.g. cardiac, renal, hepatic diseases, sickle cell disease, HIV/AIDS)
- ♣ Positive pregnancy test or breastfeeding
- ♣ Unable or unwilling to take contraceptives for women of child-bearing age
- ♣ Children weighing less than 5 kilograms
- ♣ History of hypersensitivity reaction to any medication tested or used as an alternative treatment
- ♣ Participants with history of prolonged QT conditions
- ♣ Taking regular medication, which may interfere with antimalarial pharmacokinetics or efficacy (see Annex VII)?

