#### **Dependent Variables**

- Therapeutic Efficacy of CQ+PQ

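### Haemoglobin is compared between parasite-density groups with no adjustment for age, so a difference in age mix could be read as an association with density

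*Combined protocol and SAP*

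**What the plan says.** The Statistical Analysis section plans independent-sample t-tests for two purposes. One is to "compare baseline temperature and parasitemia between children and adults". The other is to compare "mean blood Hb level at D0, D14, D28 and D42 between patients with parasitemia" at or above 10,000/µl and below it. The level is the same throughout: "All comparisons will be performed at 95% CI and significance level of 0.05". No covariate, stratum or regression model is named. The same section says that the "PP analysis method will be used to analyze secondary outcomes", but it does not list those outcomes. I treat the Hb comparison as secondary because it is plainly not the primary efficacy estimate.

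The Inclusion Criteria set a lower age limit of just over 6 months and no upper limit. Annex 10 provides for adult consent from 18 years, so adults are enrolled. The Independent Variables list begins "Age, Sex, Weight, Axillary temperature, leukocyte count", and the screening and enrolment forms (Annexes 1 and 2) record age. The only item under Dependent Variables is "Therapeutic Efficacy of CQ+PQ". Age is not used in any Hb analysis.

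**The concern.** Patients fall into the high- or low-density group by the course of their illness, not by allocation, so the two groups may differ in age. If density varies with age and Hb also varies with age, the raw difference in mean Hb mixes any density association with the difference in age mix. That could produce a significant result at a given visit with no density effect among patients of the same age. If the gradients run the other way, it could mask a real association.

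The documents hint at both links without establishing either. The plan compares parasitaemia between children and adults, which treats that link as an open question. Annex 6 sets different severe-anaemia limits for children under 12 (5 g/dl) and adults (7 g/dl), but those are severity definitions and not mean Hb by age.

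What is at stake is how a supportive comparison is interpreted. The Kaplan-Meier and per-protocol efficacy estimates do not use it. The five paired Hb t-tests compare patients with themselves, so age mix does not confound them.

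**Working it through.** **Sample size.** The plan gives no power or effect size for the Hb comparison, so the only figure to reproduce is the sample size for the failure proportion: 1.96² × 0.05 × 0.95 / 0.05² = 72.99, rounded up to 73, and 73 × 1.2 = 87.6, rounded up to 88. Both agree with Sample Size Determination ("Accordingly, a minimum of 73 patients will be enrolled"). I use 73, the number before the allowance for loss to follow-up.

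**Size of the bias, two age groups.** With no density effect at a given age, the expected crude difference is

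bias = −(adult minus child mean Hb) × (child share of high-density group − child share of low-density group).

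All inputs here are assumed. Take 40% children, Hb 1.5 g/dl lower in children, and high density in 50% of children and 30% of adults.

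- Proportion with high density: 0.4 × 0.5 + 0.6 × 0.3 = 0.38.
- Child share: 0.20/0.38 = 0.526 in the high group and 0.20/0.62 = 0.323 in the low group.
- Bias: −1.5 × 0.204 = −0.31 g/dl.

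With 40% v 30% high density and the same gap, the bias is −0.16 g/dl. With 60% v 20% and a 2.0 g/dl gap, it is −0.83 g/dl. If either factor is zero, the bias is zero. Simulation of this model (SD 1.5 g/dl, within-patient correlation 0.6, n = 73 and 88) gives rejection per visit of 11-12%, 7% and 50-56% respectively.

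**Continuous age.** A second simulation lets Hb and density change with age within childhood: 4,000 runs per scenario, n = 73, simulation error about 0.35 percentage points at 5%. Assumptions: children's ages uniform from 0.5 to 18 years, adults' from 18 to 60; adult mean Hb 13 g/dl, SD 1.5; no density effect at a given age. The probability of high density and the Hb deficit change linearly from 6 months to 18 years. Patients under 8 g/dl are removed, following the Exclusion Criteria ("Severe anemia, defined as hemoglobin (Hb) < 8 g/dl").

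| Scenario (high density youngest → adult; Hb deficit at youngest age; % children) | Unadjusted | Child/adult term | One age line | Two age slopes |
|---|---|---|---|---|
| Density unrelated to age (35%; 3 g/dl; 40%) | 5.1% | 5.0% | 5.0% | 5.1% |
| Mild (60% → 35%; 2; 30%) | 6.8% | 4.8% | 4.9% | 4.6% |
| Mild (same; 50%) | 8.9% | 5.9% | 5.9% | 5.3% |
| Middle (75% → 30%; 3; 30%) | 18.7% | 6.7% | 7.6% | 5.2% |
| Middle (same; 50%) | 26.0% | 8.4% | 7.9% | 4.6% |
| Extreme (85% → 25%; 4; 50%) | 52.0% | 15.3% | 14.6% | 5.0% |
| Reverse (25% → 55%; 3; 40%) | 11.2% | 5.6% | 6.5% | 5.2% |

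The crude gap averages 0.17-0.22 g/dl (mild), 0.43-0.54 (middle) and 0.88 (extreme), with Hb lower in the high-density group. In the reverse case it is +0.31 g/dl. If Hb is unrelated to age, the unadjusted test rejects 4.6-5.2%. At n = 88, for D0, the middle scenario with 50% children gives 30.1% unadjusted and 4.9% with two slopes.

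**Masking.** In the reverse scenario with a true difference of −1.0 g/dl, the unadjusted test detects it in 34% of runs (mean estimate −0.62). Two age slopes detect it in 75% (−0.95).

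**Other gradient shapes.** With the gradient ending at 6, 10 or 30 years, two slopes reject 4.7-6.7%, with a residual gap of up to 0.20 g/dl. A single child/adult term leaves up to 22%, and one straight line up to 19%.

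**The case against.** The strongest reply is that the plan asks a different question. It compares mean Hb between two density groups and states no age-specific or causal aim. In the simulated scenarios the crude means really do differ, so rejection is correct for that question, and harm arises only if the result is over-read. That stands: the t-test is valid for crude means. But a significance test at 0.05 at four visits invites a reported association with density, and the plan says nothing to limit that reading.

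Both age links are unproven and every input is assumed, so the results run from about 5% to well over half, and the sign can reverse. That stands too. The upper figures need steep gradients that nothing in the documents supports; under the mild one, rejection exceeds nominal by only 2-4 points.

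A simple child/adult term may be enough. It is near nominal in the mild scenarios, and it gives 4.5-5.7% throughout the two-group model, where age has only two levels. It falls short when Hb and density change within childhood.

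Two further points are fair but do not alter the conclusion. The simulation uses the 8 g/dl Hb exclusion, whereas Enrollment and Follow-up and Annex 1 use 5 g/dl; using 5 moves the extreme case from 52% to 59%. And age adjustment does not address testing at four visits: in the two-group model, at least one visit is still significant in about 14-15% of trials after adjustment.

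**Conclusion.** The concern holds as a conditional, minor point. The comparison is unadjusted across a very wide age range. If both Hb and density vary with age here, it would not separate a density association from a difference in age mix. If either link is absent, there is no bias. The plan gives no age mix, Hb SD or density split, so the simulated rejection rates show what could happen and do not predict this trial. They rest on the assumed gradients and on defining no effect as no difference at a given age. Confidence is medium. This is worth considering because the remedy is cheap; no efficacy conclusion depends on it.

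**What to change.** In Statistical Analysis, keep crude mean Hb by density group as description. Make the reported comparison at each visit a linear model of Hb on density group (10,000/µl or more v less) plus age. Give the difference with its 95% CI and call it an association.

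Enter age flexibly, in a form the observed age distribution supports and fixed without looking at Hb by density group. One option is a straight line to 18 years with a separate slope after it. Another is age bands, merged where patients are few. Fixed bands (under 5, 5-11, 12-17, 18 and over) are risky: with 30% children, at least one had fewer than 8 patients in 95-96% of runs. The under-18 slope cannot be fitted if no child is enrolled. Sex is optional. At the least, label the comparison as unadjusted description.

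The cost is one or two sentences and two or three degrees of freedom; SPSS and the age data are already in place. If Hb does not depend on age, the mean 95% CI width with two slopes rises from 1.43 to 1.47 g/dl (+3%) under the mild density gradient, 1.42 to 1.51 (+6%) under the middle and 1.43 to 1.59 (+11%) under the extreme. Four bands plus sex cost about 8-12%. If Hb does depend on age, the interval narrows: in the middle scenario from 1.61-1.62 to 1.48-1.51 g/dl.

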## ANNEX 9: Schedule of Follow-Up Activities

	day 0	day 1	day 2	day 3	day 7	day 14	day 21	day 28	day 35	day 42	any other day
PROCEDURES											
Clinical assessment	X	X	X	X	X	X	X	X	X	X	X
Temperature	X	X	X	X	X	X	X	X	X	X	X
Blood slide for parasites count	X	X	X	X	X	X	X	X	X	X	X
Hemoglobin	X					X		X		X	X
Filter paper	X			X	X	(X)	(X)	(X)	(X)	(X)	X
Drug adverse event monitoring	X	X	X	X	X	X	X	X	X	X	X
TREATMENT											
Drug to be given	X	X	X								(X)
Rescue treatment		(X)	(X)	(X)	(X)	(X)	(X)	(X)	(X)	(X)	(X)

NOTES: Parentheses denote conditional or optional activities. Rescue treatment could be given on any day, provided that the patient meets the criteria for treatment failure. Extra days are any days other than regularly scheduled follow-up days when the patient returns to the facility because of recurrence of symptoms.

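### The day-1 parasitaemia comparison between children and adults omits the day-0 count, so a baseline gap is mixed with early clearance and could be read as a difference in response, or hide one

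*Combined protocol and SAP*

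**What the plan says.** The Statistical Analysis section sets out the comparison in one clause: "Non-parametric (median) test for independent sample will be used to compare D1 parasitemia between children and adults". It names no covariate, change score or day-1/day-0 ratio.

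The same paragraph handles the baseline count separately: "Independent sample t-test will be used to compare baseline temperature and parasitemia between children and adults". The result of that test is not carried into the day-1 analysis. All tests share one error level: "All comparisons will be performed at 95% CI and significance level of 0.05". Whether it is one- or two-sided is not stated; I take it as two-sided.

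The data needed for adjustment are already planned. The Annex 9 schedule marks "Blood slide for parasites count" at every visit, including days 0 and 1. The Independent Variables list includes "asexual and/ or sexual parasites count", although no planned model uses it.

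**The concern.** A patient's day-1 count is the day-0 count multiplied by the fraction of parasites that survive the first day. On the log scale, the difference between age groups on day 1 is therefore the sum of two parts: the day-0 gap and the difference in response. A test on the raw day-1 count sees only the sum.

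There is room for a gap. Children and adults are self-formed groups. The Annex 1 screening form admits 250 to 100,000 asexual parasites/µl, a 400-fold range, while the Inclusion Criteria give only the lower limit. No document says which group starts higher, or that either does, but the plan tests for a difference and so regards one as possible.

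Two things are at stake. A significant day-1 result could not distinguish slower early clearance in one group from a higher count on arrival. A non-significant result could conceal a real difference if the slower group happened to start lower.

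**Working it through.** **1. The plan's own figures.** The sample size section is "calculated assuming 5% margin of error, 95% confidence interval (CI), and treatment failure of 5% and 20% loss to follow-up rate". The formula gives 1.96² × 0.05 × 0.95 / 0.05² = 72.99, so 73 ("a minimum of 73 patients will be enrolled"). Then 73 × 1.2 = 87.6, so 88 ("at least 88 (73 + 15) patients will be required"). Both reproduce. They concern the precision of the failure proportion only. No power is stated for the day-1 comparison, so there is none to reproduce.

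**2. Inputs.** From the documents: 73 evaluable patients, alpha 0.05, entry range 250–100,000/µl. Assumed, because the documents give nothing: a 36/37 split; log10 SD 0.6 at day 0, centred at 3.7; SD of the log10 day-0 to day-1 change (s) of 0.5, 0.8 or 1.0; a day-0 gap or a response effect of twofold (log10 2 = 0.301).

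**3. Hand check.** This ignores the limits on entry counts.

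- SD of log10 day-1 count = √(0.6² + s²) = 0.781, 1.000, 1.166.
- Twofold gap in those units = 0.385, 0.301, 0.258.
- Sample-size factor = √(36 × 37 / 73) = 4.27. The median test has relative efficiency 2/π for normal log counts, so multiply by √(2/π) = 0.798.
- Expected z = 1.31, 1.03, 0.88. Rejection rate ≈ Φ(z − 1.96) plus the negligible other tail = about 26%, 18%, 14%, with no response difference at all.
- Adjusted for day 0, the twofold gap drops out. A true twofold effect is judged against s alone: 0.301/s × 4.27 = 2.57, 1.61, 1.29, so power is about 73%, 36%, 25%.

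**4. Simulation on the same assumptions.**

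| SD of change | False positives, twofold day-0 gap, no response difference: median test | Same, rank ANCOVA | Power, twofold effect, equal day-0: median test | Same, rank ANCOVA |
|---|---|---|---|---|
| 0.5 | 27% | about 5–6% | 35% | 67% |
| 0.8 | 19% | about 5–6% | 23% | 31% |
| 1.0 | 16% | about 5–6% | 20% | 25% |

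The hand check agrees in pattern. It runs lower for the median test, most clearly for power, and slightly higher for the adjusted test at the two smaller SDs.

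**5. Opposing gap.** At SD 0.5, if the group with the slower response starts twofold lower, the median test has 7–9% power against 62–64% adjusted (day-0 centre 3.6 or 3.9).

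**6. Is it only the choice of test?** No. At SD 0.5 and a twofold gap, the Mann–Whitney test on day-1 counts rejects in 26–28% of trials. A better rank test without the covariate has the same fault.

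**7. A second set of assumptions.** Here the gap is in SD units and the day-0/day-1 log correlation runs from 0.3 to 0.8 (1,000 runs per case, Monte Carlo error up to about 3 points). With 36 versus 37 patients, a 0.5 SD gap and no response difference given day 0, the median test rejects in 11–36% and ANCOVA in 4–7%. With 26 versus 62 patients the median test rejects in 6–22%.

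**The case against.** The strongest reply is that this is a descriptive side comparison in a single-arm study. Efficacy is estimated from the failure proportion by Kaplan–Meier and per-protocol analysis, and the sample size was never set for an age comparison. Day-0 counts are tested between the same groups, so a gap would be reported beside the day-1 result. The false-positive rates need a gap that no document predicts. Most of this stands and limits the weight of the point. It does not answer it: seeing a gap in one test does not take it out of another, and a baseline t-test that finds nothing does not show that there is none.

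Three stronger readings are tempting, and the documents do not support them.

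- *That the plan reads a baseline gap as a difference in drug response.* It states no hypothesis or interpretation for this test. The most that can be said is that the result could be read that way.
- *That about half the power is lost.* From the table, the relative loss is (67 − 35)/67 = 48% at SD 0.5, but (31 − 23)/31 = 26% and (25 − 20)/25 = 20% at SDs 0.8 and 1.0. These figures also include the median test's own inefficiency. Under the second set of assumptions (73 patients split evenly, effects 0.4 to 0.8 SD), omitting the covariate alone costs between about 2% and 51% of power.
- *That this is the plan's only look at early parasitological response.* Annex 4 defines early treatment failure partly by comparing each patient's day-2 and day-3 counts with that patient's own day-0 count. Those criteria already use the baseline and feed the primary outcome.

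In fairness, the unadjusted test does not always reject less often. With a 0.5 SD gap in the same direction as a 0.5 SD effect and correlation 0.5, it rejects in 77% against 65% for ANCOVA. The excess comes from the gap and says nothing about response.

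**Conclusion.** The point holds in a limited form. The planned day-1 test cannot separate a difference in entry counts from a difference in early clearance, and it leaves out a covariate collected on every patient. Under the stated assumptions, a twofold day-0 gap raises the error rate from a nominal 5% to about 16–27%, and adjustment returns it to about 5–6%. The gain in power when there is no gap ranges from large (35% to 67%) to small (20% to 25%), depending on an SD that the documents do not give.

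The false-positive result depends on there being a gap, and its size on the assumed spread. The simulations take normal log counts, a common slope and an error-free day-0 count; counting error at day 0 would leave some bias after adjustment. The consequence is confined to a secondary comparison. The cure rate, the outcome classification and the sample size are unaffected.

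**What to change.** Replace the day-1 sentence in Statistical Analysis with: *Day-1 density will be compared between children and adults by rank ANCOVA (or a proportional-odds model) with log10 day-0 density as covariate; day-1 zero counts are kept as the lowest rank or category.* Choose one of the two models before the data are seen.

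If age as a continuous variable is of interest, fit it as a separate sensitivity model in which age replaces the child/adult term. Entering both in one model would make them strongly collinear.

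The cost is one sentence of wording. No extra patients, visits or slides are needed. One practical check is whether the analyst can fit the chosen model in the named software; the WHO spreadsheet is described as a tool for the cure-rate estimate.
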